### **2.3. Potential Risks and Benefits**

#### **2.3.1. Known Potential Risks**

The following potential risks are associated with the use of esophageal thermal regulation devices:

- Adverse tissue reaction
- Gastric distension
- Injury to the esophagus
- Harmful hypo/hyperthermia
- Injury to the trachea
- Interference with other device in the esophagus or mouth leading to esophageal trauma

#### **The following potential risks are associated with RF ablation:**

- Bleeding or infection at the puncture site(s)
- Vascular damage from mechanical shear stress on the vessel wall from the catheters
- Myocardial rupture with tamponade
- Valvular heart damage which might cause regurgitation
- Arrhythmia possibly requiring pacemaker implantation
- Venous thromboembolism
- Stroke or heart attack
- Pulmonary vein stenosis
- Acute kidney injury related to dye use during the procedure
- Atrio-esophageal fistula formation
- Death in rare cases

The following potential risks are associated with general surgery:

- Adverse reaction to anesthesia
- Hematoma or seroma at the operative site
- Failure to improve
- Persistent or worsened pain
- Infection of the wound

- Radiation exposure
- Wound dehiscence
- Vascular disorders, including thrombus
- Bronchopulmonary disorders, including emboli
- Genitourinary disorders
- Pneumonia
- Hemorrhage
- Myocardial infarction
- Death

### **3. Objectives and Purpose**

#### **3.1. Primary Objective**

The primary objective of this study is to evaluate the reduction in the occurrence and severity of esophageal injury in subjects who had a cooling tube inserted into the esophagus during radiofrequency ablation.

#### **3.2. Secondary Objectives**

The secondary objective of this study is to assess the safety of the EnsoETM and efficacy of ablation when the EnsoETM is used to regulate temperature.

#### **3.3. Exploratory Objectives**

This study will assess the EnsoETM's ease of use during RF ablation.

### **4. Study Design and Endpoints**

#### **4.1. Description of Study Design**

Single-center, randomized pilot study of esophageal temperature management using Attune Medical's EnsoETM during RF ablation vs. RF ablation without the EnsoETM.

#### **4.2. Study Endpoints**

##### **4.2.1. Primary Endpoint**

- Esophageal mucosal damage as assessed by endoscopic evaluation and graded using Zagar's modified endoscopic classification scheme.

**Table 1**

**Zargar's grading classification of mucosal injury caused by ingestion of caustic substances**

Grade 0	Normal examination
Grade 1	edema and hypermia of the mucosa
Grade 2a	Superficial ulceration, erosions, friability, blisters, exudates, hemorrhages, whitish membranes
Grade 2b	Grade 2a plus deep discrete or circumferential ulcerations
Grade 3a	Small scattered areas of multiple ulceration and areas of necrosis with brown-black or greyish discoloration
Grade 3b	Extensive necrosis

- Radiofrequency ablation of the posterior aspect of the left atrium has been shown to cause esophageal mucosal irritation which may be exacerbated by LET monitoring and/or TEE. We believe that cooling of the esophagus will lead to a reduction of esophageal damage. To date there are bench models that suggests such an esophageal sub-mucosal protection but this has not been proven in human studies.
- Providing evidence that a reduction in sub-mucosal esophageal damage using the ECD may be a precursor to reduction in atrial-esophageal fistula formation.

**4.2.2. Secondary Endpoints**

- 1) Safety of the EnsoETM placement as measured by the number of adverse events recorded
- We believe that cooling of the esophagus will lead to a reduction of esophageal damage. The use of an EnsoETM would replace LET monitoring during ablation of the posterior aspect of the left atrium. This endpoint was chosen to prove that replacing the LET monitor with a cooling catheter is a safe alternative.
- This is of primary importance as any evidence of esophageal damage or adverse events related to the use of the EnsoETM would deter any further use of this approach to Pulmonary Vein Isolation (PVI).
- 2) Altered submucosal tissue architecture as assessed by endoscopic ultrasound (EUS)
- While mucosal injury may suggest significant thermal injury to related to RF ablation there is also concern that this injury may be more of a mechanical process from TEE and LET monitoring. We aim to assess the submucosa using EUS for differentiation between superficial and deep injury which may provide further insight into the risk of atrio-esophageal fistula formation. A grading scheme has not been developed for this type of evaluation so we will assess for individual changes with pre-procedure to post-procedure comparison.

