## 7. Study Procedures and Schedule

### 7.1. Study Procedures/Evaluations

#### 7.1.1. Study Specific Procedures

- Study specific imaging will include endoscopic evaluation of the esophagus one day before surgery at the time of the pre-op Transesophageal Echocardiography (TEE) and again 1-day post-op. This will include endoscopic esophageal intubation with visual assessment of the entire esophagus and grading of lesions. Coupled with this procedure will include endoscopic ultrasound assessment of the esophagus at the level of the left atrium with specific attention to the sub-mucosal layer that separates esophagus from the cardiac tissue. The patient will undergo moderate sedation during this procedure, which will accompany the TEE.
- The ECD will be placed by trained study staff following endotracheal intubation. Proper positioning will be verified. A temperature probe will be placed to verify the patient's core temperature. The target temperature will be set to the core temperature at the beginning of the procedure. Two minutes prior to ablation on the posterior wall the target temperature will be changed to the minimum temperature setting which will allow for maximal cooling. Cooling will take place throughout the duration of posterior wall ablation. After ablation in this territory is complete the target temperature will return to the patient's core temperature. The device will be removed at the completion of the procedure by anesthesiology when there is no further need for an orogastric tube.
- LET monitoring will not be performed in the patients of the intervention group as the ECD is prohibitive. Therefore, ice lavage of the esophagus, as detailed below, will not be performed in this group.

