### **7.3.3. Surgical Procedure Visit (Visit 3)**

Subjects will undergo the RF ablation procedure within 30 days of randomization unless there is a medically valid reason to delay the procedure. The procedure is described below. Details of the procedure are referenced in section 7.1.2 of this study protocol. The investigator's procedure note will be included in the study files to gather endpoint and exploratory data.

The following day the patient will undergo repeat endoscopic evaluation in the same fashion as the prior study with moderate sedation. This will include visual assessment of the esophagus with video imaging as well as EUS at the area of interest near the left atrium at the level of the pulmonary veins.

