### **7.3.4. Follow-up Visit (Visit 3)**

The first follow-up visit will occur 12 days (+4/-4) days after the surgery procedure.

- Review medical history and medications history
- Record vital signs
- Adverse event assessment
- Assess study eligibility

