### **7.3.5. Final Study Visit (Visit 4)**

The final study visit will occur 3 months (+30/-30 days) after the surgery procedure.

- Review medical history and medications history
- Record vital signs
- Adverse event assessment
- PVI Efficacy as assessed through placement of an event monitor
- Assess study eligibility

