#### **7.3.6. Unscheduled Visit**

In addition to standard care provided during unscheduled visits, an adverse event assessment will be performed to determine whether an adverse event is present. Any adverse events will be recorded on the AE case report form.

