### **7.5. Rescue Medications, Treatments, and Procedures**

- If evidence of bleeding with placement of the ECD then the device will be removed.
- Surgical exploration and repair of esophageal fistula.
- Hemodynamic support including (Advanced Cardiovascular Life Support (ACLS) protocol will be implemented as needed.

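### The secondary safety endpoint counts adverse events of device placement, but the first scheduled adverse event assessment comes 8 to 16 days after the device is used

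*Protocol*

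**What the plan says.** Section 4.2.2 of the protocol makes "Safety of the EnsoETM placement as measured by the number of adverse events recorded" the first secondary endpoint. The accompanying text gives it high priority and ties it to showing that the cooling device can safely replace luminal esophageal temperature (LET) monitoring.

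On exposure, section 7.1.1 states: "The ECD will be placed by trained study staff following endotracheal intubation". The same section has the device taken out when the procedure is over.

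On data collection around exposure, section 7.3.3 says of the ablation visit: "The investigator's procedure note will be included in the study files to gather endpoint and exploratory data". Of the day after, it says: "The following day the patient will undergo repeat endoscopic evaluation in the same fashion as the prior study with moderate sedation". It lists no adverse event assessment for either day. Section 7.2.1 asks the endoscopist to document endoscopic and ultrasound findings.

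An adverse event assessment is a listed item at two scheduled visits. Section 7.3.4: "The first follow-up visit will occur 12 days (+4/-4) days after the surgery procedure". Section 7.3.5: "The final study visit will occur 3 months (+30/-30 days) after the surgery procedure". At unscheduled visits, section 7.3.6 says that "an adverse event assessment will be performed to determine whether an adverse event is present".

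Section 8.4 has a heading that announces the time period and frequency of event assessment, but its table holds only reporting deadlines. The protocol does not say when counting for this endpoint starts or stops. Sections 7.3.3 and 7.3.4 are both labelled Visit 3.

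**The concern.** The endpoint is about placing a device that is in the body for one procedure. Several of the device risks in section 2.3.1, such as gastric distension, injury to the esophagus or trachea and harmful temperature change, would be expected to show during use or soon after. Subjects are under general anesthesia at placement (section 7.1.2), so they cannot report symptoms at that moment.

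Two things are at stake. The first is completeness: a mild, brief event that has resolved by day 8 to 16 may never be recorded. The second is comparability. Section 4.2.2 sets the device against LET monitoring, so the two arms need the same ascertainment. As written, the record of the exposure day comes largely from an operator who cannot be blinded (section 9.2.1), with no common list of what to ask or look for. By the first scheduled assessment the subject has also had the next-day endoscopy with ultrasound, so throat or esophageal symptoms recalled then cannot be cleanly assigned to placement.

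**Working it through.** The protocol states no event rate, power or margin for this endpoint, so there is no figure of its own to reproduce. The check sets the schedule against the exposure and works out the visit windows.

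**1. Contacts from exposure onward (day 0 = ablation)**

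| Contact | Section | Adverse event assessment listed? |
|---|---|---|
| Ablation, device in and out, day 0 | 7.1.1, 7.3.3 | No; procedure note only |
| Repeat endoscopy and ultrasound, day 1 | 7.2.1, 7.3.3 | No; findings documented |
| Follow-up, day 12 ± 4 | 7.3.4 | Yes |
| Final visit, 3 months ± 30 days | 7.3.5 | Yes |
| Unscheduled visit | 7.3.6 | Yes, if one occurs |

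**2. Delay to the first scheduled assessment**

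- Earliest: 12 − 4 = day 8. Latest: 12 + 4 = day 16.
- Measured from the day 1 endoscopy: 8 − 1 = 7 to 16 − 1 = 15 days.

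**3. End of the count**

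With M as the length of 3 months in days, the last scheduled assessment falls between M − 30 and M + 30. The ratio of longest to shortest follow-up is (M + 30)/(M − 30).

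- M = 90: day 60 to day 120, ratio 120/60 = 2.00
- M = 84: day 54 to day 114, ratio 2.11
- M = 91.3: day 61.3 to day 121.3, ratio 1.98
- M = 92: day 62 to day 122, ratio 1.97

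No start is stated either. If counting began at randomization, up to 30 days before ablation (section 7.3.3), the longest period with M = 90 would be 120 + 30 = 150 days and the ratio up to 150/60 = 2.5.

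**4. How much the end of the window can matter**

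Assume that a share s of the events expected by day 60 is peri-procedural and that the rest occur at a constant rate. Relative to a subject followed to day 60, a subject followed to day 120 has an expected count of s + (1 − s) × 120/60 = 2 − s.

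- s = 0: 2.0
- s = 0.5: 1.5
- s = 0.8: 1.2
- s = 0.9: 1.1

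The shares are assumptions, because the protocol gives no event timing. The more the events cluster around the procedure, the less the final-visit window matters and the more the missing early assessment does.

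**The case against.** The strongest reply is that an event with no scheduled assessment can still be captured. The next-day endoscopy views the whole esophagus in both arms (section 7.2.1), and the image evaluator is blinded (section 9.2.1). Anesthesia includes hemodynamic monitoring (section 7.1.2), hospital records count as source data (section 10), section 8.2.1 requires evaluation whenever a subject presents with an event, and the day 12 visit includes a history review that can pick up earlier symptoms. This stands in part. A reader might infer that early events will be missed; the documents do not support that. They support a narrower statement: these routes do not form one uniform assessment, and some short-lived events may be lost or recorded unevenly.

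A reader might also infer from section 7.5 ("If evidence of bleeding with placement of the ECD then the device will be removed") that the procedure note looks for bleeding in the device arm only. It does not follow. Section 7.5 is a rule on device removal and says nothing about the note, and section 7.3.3 describes the note without restricting it to an arm.

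It can be said that sections 7.3.2 and 7.3.3 are narrative, whereas 7.3.4 and 7.3.5 are task lists, so an omission from the former proves less. That is fair, but the protocol names the assessment even for unscheduled visits, and section 8.4, where a general rule could sit, has none.

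One might want an assessment after the baseline endoscopy at Visit 2 too. That visit precedes placement and falls outside this endpoint, so the point does not extend to it.

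Finally, the counting window may be left to the statistical analysis plan, and a two-fold difference is the extreme of a window that is the same in both arms. Both statements are right. The spread in follow-up should be read as noise, not as a bias between arms. The duplicate Visit 3 label is a minor slip, since the section titles tell the two visits apart.

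**Conclusion.** The point holds in this form. For an endpoint about device placement, the first scheduled adverse event assessment common to both arms is 8 to 16 days after exposure and 7 to 15 days after a further esophageal instrumentation. Ascertainment in the days that matter most is not uniform and depends partly on an unblinded operator. How many events this would lose, or in which arm, cannot be derived from the protocol.

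The open counting window is secondary. With 3 months taken as 90 days, follow-up for the count can differ by up to 2.0-fold between subjects (1.97 to 2.11 under other month conventions). The effect on expected counts falls to about 1.1- to 1.2-fold if 80% to 90% of the events expected by day 60 are peri-procedural, which is an assumption. With 6 subjects in total, one subject's visit date can still move a raw count.

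The change should be made: the omission lies in the protocol's own visit schedule, and the correction is cheap.

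**What to change.** - In section 7.3.3, list the same structured adverse event assessment for both arms at two existing contacts: on the ablation day after recovery from anesthesia, and on the next day before the endoscope is passed. The second timing keeps symptoms after the ablation procedure apart from those caused by the repeat endoscopy.
- In section 4.2.2, state that this endpoint counts events with onset from the ablation procedure to a fixed day that every subject reaches, for example day 60, the earliest permitted final visit if 3 months is defined as 90 days. List later events separately.
- Renumber the day 12 visit, and the final visit after it, so that Visit 3 means one visit.

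The cost is one extra case report form page, repeated at contacts that already take place, and a wording change. The recorded event count will probably rise somewhat in both arms, which should be expected when the result is read. No visit or procedure is added.

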**4.2.3. Exploratory Endpoints**

- Efficacy of PVI by evaluation of rhythm at 3 months following the procedure.
  - This endpoint was chosen as a precursor to future larger studies that may focus on efficacy to ensure that PVI with EnsoETM is non-inferior to PVI with LET.
- Does the use of an EnsoETM prolong or shorten the overall ablation time?

## **5. Study Enrollment and Withdrawal**

### **5.1. Inclusion Criteria**

Patients must meet all of the inclusion criteria to be enrolled as subjects in this study.

- Subject is between ages 18 – 90 years
- Subject has an atrial or ventricular arrhythmia requiring radiofrequency ablation on the posterior aspect of the heart
- Subject is willing and able to provide informed consent
- Subject is capable of adhering to the expectations of the study protocol (e.g., attending follow-up visit)

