## 2. Introduction

### 2.1. Background Information

#### 2.1.1. Atrial and Ventricular Arrhythmias

Atrial and ventricular arrhythmias include a broad range of atypical myocardial conduction which are named based on their site of origin. Intervention for these arrhythmias include medications and/or ablation strategies. Of primary interest is the atrial arrhythmia termed atrial fibrillation. This type of arrhythmia involves multiple points of origin typically in the left atrium and the base of the pulmonary veins at the junction of the left atrium. The most common ablative strategy includes pulmonary vein isolation which involves heating (RF ablation) or cooling of the posterior aspect of the left atrium which lies near the esophagus.

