Our intention is to evaluate the use of an esophageal cooling catheter to protect the esophagus during atrial fibrillation RF ablation. This will theoretically eliminate esophageal tissue damage. As noted above, this is not a novel idea, however, there are several advantages that this device offers. The most significant of which includes a large area of

distribution of cooling effect throughout the length of the catheter as well as a large lumen. The lumen size provides more rapid thermal energy exchange thus limiting the extent of esophageal damage. There are no metal parts included in this catheter, therefore, eliminating the concern for the device acting as a wick for energy transfer and enhanced direct tissue heating. (Deneke T, 2011) The cooling catheter does not require advanced training for placement or monitoring and also acts as an oral-gastric tube during the procedure. This device is also cost effective as the cooling source is used by hospitals (nearly ubiquitously) for standard cooling blankets.

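### Section 5.1 admits ventricular arrhythmias, but the described procedure, the EUS level and the efficacy label are written for left-atrial ablation

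*Protocol*

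**What the plan says.** Eligibility is wide. Section 5.1 requires that "Subject has an atrial or ventricular arrhythmia requiring radiofrequency ablation on the posterior aspect of the heart", and nothing in the exclusions of 5.2 restricts the chamber, the arrhythmia or the lesion set. Section 2.1.1 introduces both arrhythmia types but adds "Of primary interest is the atrial arrhythmia termed atrial fibrillation".

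The later text is narrower:

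- **Intention (2.2):** to "evaluate the use of an esophageal cooling catheter to protect the esophagus during atrial fibrillation RF ablation".
- **Procedure (7.1.2, to which 7.3.3 refers for the ablation visit):** trans-septal left-atrial access, mapping and isolation of the four pulmonary veins. Further left-atrial and right-atrial lesions are added if needed. No ventricular ablation is described.
- **Primary endpoint rationale (4.2.1):** "Radiofrequency ablation of the posterior aspect of the left atrium has been shown to cause esophageal mucosal irritation".
- **Safety endpoint rationale (4.2.2):** "The use of an EnsoETM would replace LET monitoring during ablation of the posterior aspect of the left atrium".
- **EUS site (7.1.1, 7.2.1, 7.3.2, 7.3.3):** the left atrium each time. Section 7.3.3 adds the pulmonary vein level.
- **EUS reading (4.2.2):** there is no grading scheme, so "we will assess for individual changes with pre-procedure to post-procedure comparison".
- **Efficacy:** the secondary objective in 3.2 is general, "efficacy of ablation when the EnsoETM is used to regulate temperature". The endpoint in 4.2.3 is "Efficacy of PVI by evaluation of rhythm at 3 months following the procedure", and 7.3.5 also names PVI.

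**The concern.** A subject with a ventricular arrhythmia can be enrolled in full compliance with 5.1 and then meet a plan written for someone else. Followed to the letter, the protocol would image the submucosa at left-atrial level whatever site was ablated, and would record an efficacy result for a PVI that was not done.

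The EUS endpoint is the more exposed of the two. It is a within-subject comparison whose baseline is fixed the day before the ablation. A baseline at the wrong level cannot be recovered afterwards, and no analysis plan can repair it. In a study of six, one lost pair matters.

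**Working it through.** This is mainly a question of consistency, so the elements are set side by side for a ventricular subject.

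| Element | Where | Fits a ventricular subject? |
|---|---|---|
| Eligible | 5.1, 5.2 | Yes, expressly |
| Stated intention | 2.2 | No: atrial fibrillation |
| Described procedure | 7.1.2 via 7.3.3 | No: left-atrial PVI with atrial additions |
| Arm definition | 4.1, 9.2.1 | Yes: with or without the device, no chamber named |
| Zargar grade | 7.1.1, 7.2.1 | Yes: the whole esophagus is inspected |
| Adverse event count | 4.2.2 | Yes |
| Timing of second endoscopy | 7.1.1, 7.3.3 | Yes: the day after the procedure (only 7.2.1 counts from the PVI) |
| EUS level | 7.1.1, 7.2.1, 7.3.2, 7.3.3 | Not assured: left atrium in 4 of 4 places |
| Efficacy endpoint | 4.2.3, 7.3.5 | Label no; the measure (rhythm at 3 months) can be recorded |
| Ablation time | 4.2.3 | Recorded, but for a different procedure |

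For right-atrial ablation the mismatch is softer. Section 2.2 says it too can damage the esophagus, and 7.1.2 includes right-atrial lesions as additions.

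**Share of an arm.** Inputs: N = 6 (section 1) and 1:1 permuted blocks (9.2.1), with no block size given.

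- If the split is 3/3, one subject is 1/3 of an arm. Blocks of two or six guarantee this split.
- With blocks of four (an assumption), the first block gives 2/2. The next two subjects fall in the same arm with probability 2 × (2/4) × (1/3) = 1/3, which gives 4/2. One subject is then 1/4 or 1/2 of an arm.

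About a third is therefore a fair summary, exact only at 3/3.

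**Pairs at risk.** The protocol does not say how many ventricular subjects to expect. Let k be that number, taken as 0 to 3 purely as an assumption. If the EUS level misses the ablated site in each of them, the on-site pairs number 6 − k: 6, 5, 4 or 3 of 6. The same counts apply to rhythm readings that follow a PVI. The number of Zargar grades and of adverse event records stays at 6 throughout.

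The protocol states no between-arm test for EUS, so no power or error rate can be attached to these counts.

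**The case against.** The strongest reply is that the breadth is deliberate and harmless. Section 2.1.1 covers both arrhythmia types, 3.2 speaks of ablation in general, and 2.2 gives a reason to look beyond the left atrium. Section 7.1.2 is headed as standard care, so the lack of a written non-PVI procedure is missing detail rather than error. Rhythm by event monitor can be read after any ablation. The protocol also does not say where a ventricular site lies relative to the EUS level, so an off-target baseline is a possibility and not a demonstrated fact.

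Most of this stands, and it limits the point. It does not remove it: if the breadth is intended, the EUS level and the efficacy label were not written to match, and either reading needs an edit.

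A reader might go further in three ways that the text does not support.

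- **The comparator is wrong or undefined for these subjects.** Sections 4.1 and 9.2.1 define the arms only as with or without the device. The 4.2.2 sentence on LET monitoring is rationale. It is true that 4.2.2, 4.2.3, 7.1.1 and 7.1.2 treat LET monitoring as the control practice, but they do not redefine the arm.
- **The primary endpoint is compromised or its injury rate diluted.** The Zargar grade covers the whole esophagus and can be given for any subject. The protocol says nothing about injury risk after ventricular ablation, so a dilution figure would be invented.
- **All non-left-atrial cases are equally out of place.** The right-atrial text in 2.2 and 7.1.2 contradicts that.

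**Conclusion.** The inconsistency is real and complete for ventricular ablation, and partial for right-atrial ablation. It touches one secondary endpoint (the EUS comparison) and the exploratory endpoints (rhythm and ablation time). What it threatens is comparability between subjects who had different procedures. With random allocation it is not a source of systematic bias between the arms.

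Its size is about a third of an arm per ventricular subject. The EUS loss rests on the assumption that the left-atrial level is away from the ablated site. With no such subject enrolled there is no effect. Severity is low, but the mismatch is avoidable before enrolment and, for the EUS baseline, not repairable afterwards.

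**What to change.** Reconcile 5.1 with 2.2, 4.2.3, 7.1.1, 7.1.2, 7.2.1, 7.3.2, 7.3.3 and 7.3.5. There are two routes, and the choice of population belongs to the investigators.

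1. **Limit 5.1.** Require that the planned ablation be the left-atrial procedure set out in 7.1.2. This is a change of one line. The cost is a slightly smaller recruitment pool and no data on other arrhythmias.
2. **Keep 5.1 wide.** (a) Set the EUS level, before and after, to the planned ablation site in the four sections that now name the left atrium. (b) Reword the efficacy endpoint in 4.2.3 and 7.3.5 as rhythm at 3 months after the index ablation, which agrees with 3.2. This takes edits in six sections, and the subjects would still have had different procedures, so rhythm and ablation time should be reported with the procedure named.
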